**Principal investigator:**

**[name], MPH  
Assistant [name]  
The University of Arizona Cancer Center  
[name]  
[name]  
P- [contact]  
F- [contact]  
[contact]**

**Title of Study:** A single arm Phase II trial to assess association of BRCA1 protein expression with overall response rate in patients with metastatic breast cancer on pegylated liposomal doxorubicin

**Primary Objective:** To evaluate if low BRCA1 protein expression has a preferential effect on response when metastatic breast cancer patients are treated with a DNA damaging chemotherapy agent.

**Secondary Objective:** To evaluate if low BRCA1 protein expression has a preferential effect on tumor progression when metastatic breast cancer patients are treated with a DNA damaging chemotherapy agent.

**Primary Endpoint:** To correlate BRCA1 protein expression, as measured by IHC with overall response rate for metastatic breast cancer patients treated with pegylated liposomal doxorubicin. The overall response rate is defined as the percentage of evaluable patients who achieve complete response (CR) or partial response (PR) as measured by RECIST 1.1 on CT or PET/CT as the best overall response

**Secondary Endpoint:** To correlate BRCA1 protein expression, as measured by IHC with median progression free survival for metastatic breast cancer patients treated with pegylated liposomal doxorubicin. The progression free survival is measured as the times from the start of pegylated liposomal doxorubicin to the time the patient is first recorded as having disease progression or die

### **Background information:**

It is well known that women with germline mutations in BRCA1 or BRCA2 are at increased risk for developing various malignancies. Defective homologous recombination, which occurs as a result of these mutations, impairs the normal repair mechanism for DNA double stranded breaks (DSB). Alternative error-prone, potentially mutagenic DNA repair mechanisms like non-homologous end joining (NHEJ) and single stranded annealing (SSA) take over and lead to genomic instability. This “homologous recombination deficiency” (HRD) may be a critical pathway in development of cancers, and also make the affected cells more susceptible to DNA damaging drugs like alkylators, anthracyclines and platinum agents. Somatic mutations in BRCA1 and BRCA2 do not occur frequently in sporadic breast cancer but potentially any (somatic) inactivation of the genes could result in loss of their phenotypic expression. A phenomenon called “BRCAness” has been reported in sporadic cancers that do not have the germline mutations in BRCA1 or BRCA2, but display similar inactivation of the BRCA related genes and defective HRD. The reported incidence in the literature ranges from 15% to 50%. The incidence varies with the histology, with higher percentage of triple negative tumors expressing “BRCAness” signature (30-60%) compared to hormone receptor positive tumors (5-20%). Detecting this underlying tumor cell defects in effective DNA repair could provide crucial information in attempting to “personalize” treatment for breast cancer patients, directing DNA targeted therapy to such patients.

There have been published studies assessing HRD (primarily involving BRCA1 and BRCA2) in breast cancer and associating it with response to neoadjuvant chemotherapy. Rodriguez et al reported higher sensitivity to anthracycline-based therapies in patients whose tissue samples had a defective DNA repair gene signature. In a study with similar design by Lips et al, about half of triple negative tumors were found to have BRCA1 inactivation but it was only modestly predictive of response. However, in ER positive tumors a BRCA2 like-aCGH

was found in a surprising proportion of this neoadjuvant population (43%) and was strongly predictive of excellent response to chemotherapy. Vollenbergh et al reported association of BRCA1 signature and benefit from high dose platinum-based chemotherapy. They reported improved recurrence free survival and overall survival for patients who had BRCA1 like aCGH when they received high-dose platinum treatment. Currently, there is no standard assay to detect HRD. Some early efforts have been reported in the literature including array comparative genomic hybridization (aCGH), RT-PCR, multiplex ligation-dependent probe amplification and immunohistochemistry (IHC). The most frequently used and reported assay is DNA based aCGH to assess copy number variation of BRCA1 or BRCA2 or both. All the published studies have defined “BRCA1 like signature” independently and currently, there is no standardized definition. Moreover, DNA or RNA based approaches require fresh frozen tissue for optimal results, expertise in genomic analysis and interpretation (which is not readily available in non-academic setting) and time for tissue analysis and interpretation. To date, those techniques are not yet ready for utilization on a day to day basis where decisions regarding treatment are time-sensitive. IHC can be rapidly translated into current clinical practice due to the ability to use FFPE tissue which is readily available in all academic and community practices. Furthermore, after an IHC method has been validated it can be replicated in standard clinical testing laboratories and easily added to the standard breast diagnostic IHC panel (ER, PR, HER2 and Ki 67).

In collaboration with the Tissue Core and Cellular/Molecular Analysis core (TACMASS) at the University of Arizona Cancer Center we have validated a BRCA1 IHC assay, which can detect BRCA1 protein expression in breast tumors samples. Pegylated liposomal doxorubicin is frequently used in the salvage treatment of patients with metastatic breast cancer. It is a DNA damaging chemotherapy agent which has been reported to have a 25% overall response rate and 2.5 months median progression free survival in the salvage treatment of metastatic breast cancer. It has been shown to be safe in patients who have received prior anthracycline treatment.

As far as we are aware, there have not been any studies or reports evaluating BRCA1 expression prospectively in the context of relative benefit from DNA damaging agents. We propose such a trial in which patients with metastatic breast cancer who will receive pegylated liposomal doxorubicin as a salvage treatment. The goal is to discern whether there appear to be effects on relative benefit from this agent, which can be determined by assaying BRCA1 protein expression on tumor specimens available from the patient.

**Study Design:** This study is a prospective single arm Phase II trial to assess the association of BRCA1 protein expression with overall response rate in patients with metastatic breast cancer treated with pegylated liposomal doxorubicin

**Study Centers:** University of Arizona Cancer Center, University of New Mexico Cancer Center

**Number of Patients:** We plan to consent 50 to 60 patients with the goal of accruing a total of 50 patients into this prospective single arm, Phase II trial.

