## Schema

**Statistical Methods:** This study is a prospective single arm Phase II trial to assess the association of BRCA1 protein expression to overall response rate when metastatic breast cancer patients are treated with pegylated liposomal doxorubicin. We plan to consent 50 to 60 patients with the goal of enrolling a total of 50 patients to this study. It is anticipated that 30% of patients will have low BRCA1 protein expression and therefore anticipate approximately a 35 to 15 patient split for intact BRCA1 to low BRCA1 protein expression.

**Definition of primary endpoint:** Response rate is defined as the percentage of evaluable patients who achieve complete response (CR) or partial response (PR) as measured by RECIST 1.1 on CT or PET/CT as the best overall response.

**Definition of secondary endpoints:** Progression free survival will be measured as the times from the start of pegylated liposomal doxorubicin to the time the patient is first recorded as having disease progression or dies. If a patient does not progress or die while being followed via tumor assessment, progression-free survival will be censored at the time of last disease assessment.

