### **Preliminary data:**

In collaboration with the Tissue Core and Cellular/Molecular Analysis core (TACMASS) at the University of Arizona Cancer Center (UACC) we have validated a BRCA1 IHC assay in breast tumor samples. Antigen retrieval techniques and antibody titers have been optimized using the Genscript A00490 Rb polyclonal antibody. We retrospectively analyzed 45 breast tumor samples, 37 of which were triple negative tumors. Low BRCA1 protein expression was found in 43% of the triple negative tumors. This result is in concordance with other reported series of BRCA1 signatures using DNA and/or RNA based approaches. Clinical information was available in 37 patients. A total of 21 patients received anthracycline based chemotherapy of which 13 had intact BRCA1 and 8 had low BRCA1 protein expression. Fewer breast cancer recurrences were seen in patients with low BRCA1 protein expression (2/8) compared to those with intact BRCA1 protein expression (6/13). However, in this small sample of assessed tumors, chemotherapy was administered at different time points (neoadjuvantly or adjuvantly) and follow up was not standardized in all patients. Nevertheless, these results support our hypothesis that low BRCA1 protein expression predicts increased sensitivity to treatment with DNA damaging chemotherapy.

DNA damage leads to the early activation of BRCA1 where it plays a vital role in the homologous recombination (HR) repair of double stranded DNA. Unlike other mechanisms of DNA repair, BRCA1 mediated HR tends to be conservative and error free. Thus cells deficient in BRCA1 protein are uniquely susceptible to agents/mechanisms which cause DNA damage due to their inability to repair through HR. We propose to test the clinical utility of BRCA1 quantification by immunohistochemical (IHC) analysis for predicting response to chemotherapy in the prospective setting. Our **hypothesis** is that low BRCA1 protein expression in primary breast tumors of metastatic breast cancer patients predicts improved response to DNA damaging chemotherapy in the metastatic setting.

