## 3. Trial Design

### 3.1. Study Endpoints

**Primary Endpoint:** To correlate BRCA1 protein expression, as measured by IHC with overall response rate for metastatic breast cancer patients treated with pegylated liposomal doxorubicin. . The overall response rate is defined as the percentage of evaluable patients who achieve complete response (CR) or partial response (PR) as measured by RECIST 1.1 on CT or PET/CT as the best overall response

**Secondary Endpoint:** To correlate BRCA1 protein expression, as measured by IHC with median progression free survival for metastatic breast cancer patients treated with pegylated liposomal doxorubicin. The progression free survival is measured as the times from the start of pegylated liposomal doxorubicin to the time the patient is first recorded as having disease progression or dies.

3.2. **Study Design** This study is a prospective single arm Phase II trial to assess the association of BRCA1 protein expression with overall response rate in patients with HER2 negative metastatic breast cancer treated with pegylated liposomal doxorubicin. Patients who qualify for enrollment into the study will receive pegylated liposomal doxorubicin as a single agent intravenous at 30mg/m^2 every 21 days

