### 8.3. **Analytic plan for secondary objective:**

**Definition of secondary endpoints:** Progression free survival will be measured as the times from the start of pegylated liposomal doxorubicin to the time the patient is first recorded as having disease progression or dies. If a patient does not progress or die while being followed via tumor assessment, progression-free survival will be censored at the time of last disease assessment.

We will calculate the median progression free survival in patients with low BRCA1 and normal BRCA1 protein expression. Median progression free survival will be estimated by Kaplan-Meier methodology.

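### Response and PFS are reported by BRCA1 class only, so a receptor-subtype difference could create or mask an apparent BRCA1 effect; a descriptive breakdown by subtype would expose it cheaply.

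*Combined protocol and SAP*

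**What the plan says.** The Synopsis background links the BRCAness signature to receptor subtype. It cites a "higher percentage of triple negative tumors expressing “BRCAness” signature (30-60" percent), "compared to hormone receptor positive tumors (5-20" percent). The two ranges do not overlap. Section 1.2, under Preliminary data, reports on the trial's own immunohistochemistry (IHC) assay: "Low BRCA1 protein expression was found in 43% of the triple negative tumors". It gives no rate for the remaining samples.

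Sections 1.3 and 4.2 restrict receptor status only by excluding HER2-positive tumours, so triple-negative and hormone-receptor-positive patients may both enter. There is no quota or stratum.

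Section 2 asks whether low BRCA1 has a preferential effect on response and on progression. Section 3.1 words the primary endpoint as "To correlate BRCA1 protein expression, as measured by IHC with overall response rate for metastatic breast cancer patients treated with pegylated liposomal doxorubicin". Section 8.2 gives a response rate with an exact interval in each BRCA1 class. Section 8.3 says "We will calculate the median progression free survival in patients with low BRCA1 and normal BRCA1 protein expression", by Kaplan-Meier. Neither section stratifies, adjusts or tabulates by ER/PR status, and the pretreatment list in 5.1 does not name it. ER and PR appear only as members of the routine diagnostic panel, in the Synopsis background and in section 1.2.

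**The concern.** The objective is about BRCA1 itself. If low-BRCA1 patients are more often triple-negative, and triple-negative disease responds differently to this drug, the two cohort response rates will differ even if BRCA1 does nothing. A subtype difference in the other direction could hide a real BRCA1 effect. The same applies to progression-free survival.

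Section 8.2 says the low-cohort data will form the basis of a larger trial of BRCA1 as a predictor. If subtype explains the contrast, that trial would start from the wrong hypothesis. As written, the plan gives the reader no means of telling the two explanations apart.

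**Working it through.** **The plan's own figures.** The Synopsis statistical methods say "It is anticipated that 30% of patients will have low BRCA1 protein expression", "with the goal of enrolling a total of 50 patients to this study", and "anticipate approximately a 35 to 15 patient split for intact BRCA1 to low BRCA1 protein expression". These agree: 0.30 × 50 = 15 low, leaving 35 intact.

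**Inputs.**
- Low rate in triple-negative tumours, *a*: 30-60%, midpoint 45% (Synopsis background); 43% by the trial's assay (section 1.2).
- Low rate in hormone-receptor-positive tumours, *b*: 5-20%, midpoint 12.5% (Synopsis background).
- Overall share low, *L*: 30%.
- Triple-negative share enrolled, *t*: not stated; solved from *L*, or assumed.
- Response gap between subtypes, *g*: not stated; assumed at 10, 20 and 30 points, either direction.

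Every patient is treated as low or intact, as the planned split does; the indeterminate class in section 1.2 is ignored.

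**Formulas.**
- *L* = *ta* + (1 − *t*)*b*, so *t* = (*L* − *b*)/(*a* − *b*)
- Triple-negative share of the low cohort = *ta*/*L*
- Triple-negative share of the intact cohort = *t*(1 − *a*)/(1 − *L*)
- Shift in the crude contrast with no BRCA1 effect = *g* × (difference between those two shares)

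**Mid-range case at the planned 30% low.**
- *t* = (0.30 − 0.125)/(0.45 − 0.125) = 0.538
- Low cohort: 0.538 × 0.45/0.30 = 0.808, about 12 of 15
- Intact cohort: 0.538 × 0.55/0.70 = 0.423, about 15 of 35
- Imbalance: 38.5 points
- Shift: 3.8, 7.7 and 11.5 points for gaps of 10, 20 and 30 points

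**Other rates, still at 30% low.**

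| *a* / *b* | *t* needed | Triple-negative in low | Triple-negative in intact | Imbalance (points) |
|---|---|---|---|---|
| 43% / 12.5% | 57.4% | 82.2% | 46.7% | 35.5 |
| 43% / 20% | 43.5% | 62.3% | 35.4% | 26.9 |
| 60% / 20% | 25.0% | 50.0% | 14.3% | 35.7 |
| 60% / 5% | 45.5% | 90.9% | 26.0% | 64.9 |
| 30% / any | 100% | 100% | 100% | 0 |

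The last row is the limit: if only 30% of triple-negative tumours are low, 30% low overall requires an all-triple-negative trial and there is nothing to confound.

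**Fewer triple-negative patients.** Take *t* at 20-30% (assumption), a 15-point gap (assumption) and the full cited ranges for *a* and *b*.
- Smallest shift: *t* = 20%, *a* = 30%, *b* = 20%. Low 0.06/0.22 = 0.273; intact 0.14/0.78 = 0.179; 15 × 0.093 = 1.4 points.
- Largest shift: *t* = 30%, *a* = 60%, *b* = 5%. Low 0.18/0.215 = 0.837; intact 0.12/0.785 = 0.153; 15 × 0.684 = 10.3 points.

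These two cases imply 22.0% and 21.5% low overall, not the planned 30%.

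**Precision for comparison.** With 15 against 35 patients and 25% response in both, the approximate 95% half-width for a crude difference is 1.96 × √(0.25 × 0.75 × (1/15 + 1/35)) = 26 points.

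No shift is computed for progression-free survival, because the documents give no PFS by subtype.

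**The case against.** Four points can be made on the other side.

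- **The link is not shown for this assay.** The cited ranges describe a signature, not a nuclear IHC score, and the protocol itself says the signature has no standard definition. This stands in part. The 43% from the trial's assay supports the triple-negative side, and section 1.2 calls it concordant with DNA- and RNA-based series, but there is no IHC rate for hormone-receptor-positive tumours. A reader might infer that the low cohort is certain to be dominated by triple-negative disease. The documents do not support that: at 30% and 20% low with 25% triple-negative patients, the shares are 33% and 23%.
- **The bias needs figures from outside.** This stands. The documents give one overall response rate of 25% for the drug and none by subtype. With no gap there is no bias, and the direction is unknown. A reader might also infer a narrow band of bias from one mid-range case, but the cited ranges alone move it about sevenfold.
- **Nothing is formally compared.** Section 8.2 plans no test or difference between cohorts and calls the low-cohort data hypothesis-generating, and a 26-point half-width exceeds every shift computed here. This limits the consequence. It does not remove the concern, because the stated objective invites the reader to set the two rates side by side, and bias does not show in the interval.
- **Stratifying 15 patients is close to uninformative.** This stands for any formal estimate, but not for a cross-tabulation, which shows how far BRCA1 class and subtype overlap.

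**Conclusion.** The point holds as a gap in the analysis plan, not as an error in a stated figure. By the protocol's own rates the low cohort is likely to hold more triple-negative disease (about 81% against 42% at mid-range and 30% low), and nothing in 8.2 or 8.3 separates subtype from BRCA1. The resulting shift in the crude response contrast is about 3.8 to 11.5 points for assumed subtype gaps of 10 to 30 points, or 1.4 to 10.3 points for a 15-point gap with 20-30% triple-negative patients. Its sign is unknown.

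This rests on the signature rates carrying over to the IHC classes and on assumed response gaps. A reader might infer that the go/no-go decision is compromised too. It is not: the Simon rule is applied to the intact cohort alone, as enrolled, and its exact type I error (0.098) and power (0.901) agree with the plan.

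**What to change.** - **Section 5.1:** record ER and PR status at registration from the existing pathology report.
- **Section 8.2:** tabulate response by BRCA1 class within triple-negative and within hormone-receptor-positive disease, with counts. Give a subtype-stratified BRCA1 contrast, such as a Mantel-Haenszel risk difference, beside the crude one, labelled descriptive.
- **Section 8.3:** show Kaplan-Meier curves by BRCA1 class within each subtype, on the same descriptive footing.
- **Interpretation:** state in advance that a crude difference will not be attributed to BRCA1 unless the within-subtype results point the same way.

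The cost is two data items and a few extra displays, with no change to sample size, eligibility or treatment. The downside is small cells: at mid-range about 3 of the 15 low-BRCA1 patients would be hormone-receptor-positive (15 × 0.192 = 2.9), so the stratified estimate will be very imprecise and must not be used as a formal test.

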**Main Criteria for Inclusion/Exclusion:**

To be eligible for inclusion, each patient must have:

- Metastatic breast cancer and have formalin-fixed, paraffin-embedded tumor available for testing BRCA1 protein expression
- Adults over 18 years of age
- Have resolution of all acute toxic effects of any prior chemotherapy or radiotherapy to NCI CTC grade  $\leq 1$  prior to study registration.

[figure not shown]
- Be informed of the investigational nature of this study and provide written informed consent in accordance with institutional and federal guidelines prior to study specific screening procedures
- Be willing and able to comply with the treatment plan, scheduled clinic visits, laboratory and oncological tests and other study procedures
- Have a ECOG performance status of 0 – 2
- Measurable disease by CT by RECIST 1.1 to evaluate response. Patients with bone only lesions are also eligible to enroll. Criteria to monitor for response will be based on non-target lesions per RECIST criteria
- Adequate bone marrow function defined as platelets  $\geq 100 \times 10^9$  cells/L, neutrophils  $\geq 1.5 \times 10^9$  cells/L, white blood cells (WBC)  $\geq 3.0 \times 10^9$  cells/L and a hemoglobin  $\geq 90$  gm/L
- Liver function tests (AST and/ or ALT) should be  $\leq 2$  x upper limit of normal (ULN, defined as per laboratory where blood testing is done), total bilirubin  $\leq 1.5$  x ULN (except for patients with liver metastases, ALT and/or ALT  $\leq 5$  times the upper limit of normal is accepted)
- Patients who are already on pegylated liposomal doxorubicin will be eligible to participate in this study as long as they meet the other inclusion/exclusion criteria and can sign informed consent

**Exclusion Criteria** The following will exclude patients from study participation Myocardial infarction within 6 months of registration Brain metastases unless documented to be controlled post completion of local therapy (surgery and/or radiation therapy) for at least four weeks prior to registration Pregnant or breast feeding women. Women with child bearing potential must use effective measures to prevent pregnancy while receiving pegylated liposomal doxorubicin Have a concurrent active non-breast malignancy except for non-melanoma skin cancer Have a concurrent active non-breast malignancy except for non-melanoma skin cancer Her2 positive tumors as defined by FDA guidelines (3+ immunohistochemical staining, defined as uniform, intense membrane staining of more than 10% of invasive tumor cells, and for cases with 2+ staining showing gene amplification by FISH, expressed as a ratio of more than 2 when comparing HER-2 gene and chromosome 17 fluorescent signals)

**Intervention:** Patients with metastatic breast cancer treated at the University of Arizona Cancer Center and University of New Mexico Cancer center will be enrolled in this trial. Patients whose treatment for their tumor includes liposomal doxorubicin are eligible to take part in this study. Their primary tumors will be obtained for evaluation of BRCA1 protein expression. When primary tumor is not available, paraffin embedded metastatic tumor will be tested for BRCA1 protein expression. Patients will receive pegylated liposomal doxorubicin intravenously at  $30\text{mg}/\text{m}^2$  every 21 days.

**Duration of Intervention:** Patients will get a baseline PET/CT or CT chest/abdomen/pelvis scan prior to receiving pegylated liposomal doxorubicin. We will repeat the same imaging scan at 9-12 weeks to evaluate response by RECIST 1.1. Pegylated liposomal doxorubicin will be stopped if there is evidence of disease progression. Also, it will be discontinued if there is development of persistent  $\geq$  grade 3 fatigue or non-reversible  $\geq$  grade 4 hematological or renal or liver abnormalities or if the patient chooses.

